7.2.2. Inclusion and Exclusion Criteria

Listings will present inclusion and exclusion criteria for each subject in the Enrolled Set.

7.2.3. Summary of Subject Characteristics

The following subject characteristics will be summarized in a table: demographics, baseline characteristics, medical history, cancer diagnosis, sites of metastases as identified from pre-treatment CT/MR and bone scans (lung, liver, abdomen other than lung, pelvis, bone, other) and the number and percentage of subjects receiving different types of prior cancer treatment (radiation, drug or biologic, surgical). Previous exposure to I 131 MIBG, identified in the subject's cancer history, whether by participation in an earlier study of iobenguane I 131 or other I 131 MIBG preparations will be summarized and presented in a listing. The Safety Set will be used for this summary.

7.2.3.1. Demographics and Baseline Characteristics

Demographics (sex, race and ethnicity) and baseline characteristics (age at enrollment [defined as $\text{age} = \text{floor}(\frac{\text{intck}(\text{'month'}, \text{birthdate}, \text{consentdate}) - (\text{day}(\text{consentdate}) < \text{day}(\text{birthdate}))}{12})$], height at screening, weight at screening and body surface area) will be summarized and listed.

7.2.3.2. Cancer Diagnosis, Medical History and Prior Cancer Treatment

Cancer diagnosis and sites of metastases will be summarized by the number and percent of subjects reporting the preferred term using Medical Dictionary for Regulatory Activities[®] (MedDRA) version 19.0 and listed. Medical history data and prior cancer treatments will be tabulated and provided in listings. This information will be summarized for the Safety Set.

7.3. Subject Medications and Study Drug Administration

7.3.1. Study Drug Administration/Exposure

Study drug administration will be summarized by Imaging Dose and Therapeutic Dose for the Safety Set. A listing of the study drug administration data will be presented. The amount of each Therapeutic Dose will be presented as absolute amount of radioactivity (mCi), as body weight normalized (mCi/kg) and as body surface area (BSA) normalized (mCi/m²) using the DuBois formula:

$$\text{BSA} = w^{0.425} \times h^{0.725} \times 0.007184,$$

where w is body weight in kilograms and h is height in centimeters. The amount of the Imaging Dose will be presented as absolute amount of radioactivity (mCi). The total exposure for each subject (defined as the sum of all therapeutic and imaging doses) will be summarized. For subjects who received more than one imaging dose, all doses of study drug will be included in that subject's total exposure.

The injection volume (mL) will be summarized for each dose and for the sum of the two therapeutic doses.

Dosing will be tabulated by the number of doses received (imaging and therapeutic doses), the time in days from the imaging to the first therapeutic dose, and the time in months from the first to the second therapeutic dose.

7.3.2. Concomitant and Prior Medications, other than Antihypertensives

Concomitant medications and prior medications will be coded according to the World Health Organization (WHO) Drug Dictionary v. March 2016 and summarized in tables by ATC4 code as well as in listings.

Medications will be assigned to one or more study periods (prior medications or concomitant medications) based on the medication start and stop dates relative to the study drug dosing. For example, medications that were started and stopped before the date of the imaging dose will be classified as prior medications only, while medications started before the imaging dose and either stopped after the imaging dose or indicated as "ongoing" will be assigned as both prior and concomitant medications. Medications started on or after the date of the imaging dose will be

classified as concomitant medications. A given medication can therefore be assigned to one or more study periods in the tabular summaries, depending on its start and end dates.

Because antihypertensive medications are a measure of efficacy in this study, they will be tabulated and listed separately. Medications that could be used to treat hypertension, but were being used to treat other non-hypertensive indications, will be listed under the concomitant and prior medications listing rather than the hypertensive medication listing. Analgesic medications reported for treatment of tumor pain will also be tabulated and listed separately.

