APPENDIX IV

QUALITY OF LIFE AND SYMPTOMS QUESTIONNAIRES

NIH Quality of Life and Symptoms Questionnaire for Pheochromocytoma and Paraganglioma

Subjects sometimes report that they have the following symptoms or problems related to their pheochromocytoma or paraganglioma. Please indicate the extent to which you have experienced these symptoms or problems related to your pheochromocytoma or paraganglioma during the last two weeks. Please answer by circling the number that best applies to you.

During the last two weeks: 1) Have you experienced an increase in your blood pressure?	Not at all 1	A little 2	Quite a bit 3	Very much 4
2) Have you experienced a decrease in your blood pressure?	1	2	3	4
3) Have you experienced an increase in your heart rate?	1	2	3	4
4) Have you experienced a decrease in your heart rate?	1	2	3	4
5) Have you experienced anxiety or nervousness?	1	2	3	4
6) Have you experienced any sweating?	1	2	3	4
7) Have you experienced paleness?	1	2	3	4
8) Have you experienced any hot flashes or flushing?	1	2	3	4
9) Have you experienced any headaches?	1	2	3	4
10) Have you experienced any dizziness?	1	2	3	4
11) Have you experienced any panic attacks also known as				
'sudden experience of intense anxiety'?	1	2	3	4
12) Have you experienced any tremors or shaking?	1	2	3	4
13) Have you experienced any numbness?	1	2	3	4
14) Have you experienced any nausea?	1	2	3	4
15) Have you experienced any vomiting?	1	2	3	4

NIH Quality of Life and Symptoms Questionnaire for Pheochromocytoma and Paraganglioma (continued)

During the last two weeks: 16) Have you experienced any weakness?	Not at all 1	A little 2	Quite a bit 3	Very much 4
17) Have you experienced any fatigue?	1	2	3	4
18) Have you experienced increase in energy level?	1	2	3	4
19) Have you experienced a decrease in energy level?	1	2	3	4
20) Have you experienced any increase in weight?	1	2	3	4
21) Have you experienced any decrease in weight?	1	2	3	4
22) Have you experienced any warmth or heat intolerance?	1	2	3	4
23) Have you experienced any visual changes?	1	2	3	4
24) Have you experienced any changes in bowel function?	1	2	3	4
25) Have you experienced any seizures?	1	2	3	4
26) Have you experienced any pain (other than chest pain)?	1	2	3	4
27) Have you experienced chest pain?	1	2	3	4
28) Have you experienced palpitations?	1	2	3	4

At Screening #2 the additional question will be asked:

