7.4.2. Calculation of the Primary Endpoint

Criteria for Meeting the Primary Endpoint

Subjects must:

1. Receive an Imaging Dose
2. Receive at least one Therapeutic Dose
3. Have a reduction of each pre-therapeutic dosing (baseline) antihypertensive medication $\geq 50\%$ for a minimum of six consecutive months beginning during the 12-Month Efficacy Phase of the study, during which no new, long-term antihypertensive medication is introduced and maintained for longer than 14 days.

Considerations

1. The introduction of a new, transient (i.e., duration ≤ 14 days) antihypertensive medication regimen at any point during the study will not disqualify a subject from being able to achieve the primary efficacy endpoint. Short duration therapy may be instituted to address an acute increase in blood pressure that might be associated with a transient increase in catecholamine release secondary to a variety of factors including tumor cell death. On the contrary, the primary outcome measures chronic control of hypertension necessitated by long term catecholamine secretion by the active tumor.
2. A transient (i.e., duration ≤ 14 days) dose increase over the baseline dose of an existing antihypertensive medication regimen at any point during the study will not disqualify a subject from being able to achieve the primary endpoint. Existing antihypertensive therapy may be increased for a short duration to address an acute increase in blood pressure that might be

associated with a transient increase in catecholamine secretion secondary to a variety of factors including tumor cell death.

3. The introduction of a new, long-term (i.e., duration > 14 days) antihypertensive medication regimen after receiving a therapeutic dose will disqualify a subject from being able to achieve the primary endpoint while the subject is still taking any dose of the new medication. If the new long-term antihypertensive medication is discontinued, the start date for assessment of the primary endpoint is the date when both the new medication is discontinued and the baseline antihypertensive medications are reduced $\geq 50\%$.
4. New long-term antihypertensive medications introduced before Therapeutic Dose #1 is administered are considered part of the baseline antihypertensive medication regimen that must be reduced by at least 50% for achieving primary endpoint.

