5. A long-term (i.e., duration > 14 days) increase in dose over the baseline dose of an existing antihypertensive medication regimen after receiving a therapeutic dose will not disqualify a subject from being able to achieve the primary endpoint if all antihypertensive medications are reduced to a level of 50% or below the baseline dose for at least six consecutive months in duration, since the increase may have been made before a tumor response was obtained. The introduction of a new antihypertensive medication with a duration of >14 days will be considered as the end of a benefit duration period. The start date for the duration of response is the date that the last antihypertensive medication is reduced to the level of 50% or below the baseline dose.
6. The introduction of an antihypertensive medication regimen or increase in existing antihypertensive medication regimen that occurs after the subject has already met the primary endpoint (i.e., had a $\geq 50\%$ reduction of all antihypertensive medications for at least six consecutive months) will not disqualify the subject from achieving the primary endpoint.

Calculation of Duration of Response

The six-month duration of the primary endpoint response begins on the date during the 12-Month Efficacy Phase when all baseline antihypertensive medications have been reduced by at least 50% and any new medications are discontinued (the date post-therapeutic dosing when the reduction of the last antihypertensive medication reduced by at least 50% or the new medication is discontinued) and ends once six consecutive months (i.e., 168 days) duration of sustained $\geq 50\%$ reduction has been achieved, regardless of the phase of the study during which the end date of the response occurs (i.e., 12-Month Efficacy Phase vs. Long-Term Follow-Up Phase).

The end date for which the duration of the $\geq 50\%$ reduction of all antihypertensive medications is determined as the earlier of:

- a. the date that the subject no longer meets the criteria of having a $\geq 50\%$ reduction of all baseline antihypertensive medications (i.e., the starting date of a new long-term continuing antihypertensive medication or a dose change in an existing regimen of antihypertensive medication that exceeds the $\geq 50\%$ reduction of the baseline dose that is greater than 14 days in duration and continues without a reduction to the $\geq 50\%$ level)

OR

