7.7. Procedures for Handling Dose and Dosing Frequency (Anti-hypertensive and Pain Medications)

In order to standardize the reporting of doses and dose frequency, all unique values of these fields from the raw concomitant medication dataset will be exported to an Excel spreadsheet where the total daily dose will be added to create a coded dataset. The Excel sheet will be prepared by the Sponsor and used in the creation of analysis datasets. This standardization will be applied to medications identified as anti-hypertensive medications on the CRF and, separately, to medications identified as analgesics with indications for pain relief

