7.9. Sensitivity Analysis

A sensitivity analysis will be performed on the primary endpoint where at least six months of the duration of clinical benefit is required to be completed within the 12-month efficacy period. An additional sensitivity analysis will treat subjects who begin a new antihypertensive medication following therapeutic dosing that continues for at least 14 days as non-responders.

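### A new long-term blood-pressure-lowering drug recorded for a non-hypertensive indication may escape both the primary endpoint's new-drug rule and its sensitivity analysis; a class-based sensitivity analysis would close the gap.

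*SAP*

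**What the plan says.** SAP 7.3.2 explains why antihypertensives are handled apart from other drugs: "Because antihypertensive medications are a measure of efficacy in this study, they will be tabulated and listed separately". It then sorts dual-purpose drugs by use: "Medications that could be used to treat hypertension, but were being used to treat other non-hypertensive indications, will be listed under the concomitant" and prior medication listing, not the antihypertensive one.

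SAP 7.7 describes how total daily doses are standardized for the analysis datasets. For blood pressure drugs, this is "applied to medications identified as anti-hypertensive medications on the CRF".

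The endpoint rules in SAP 7.4.1 and 7.4.2 are written in terms of antihypertensive medication. Success requires a reduction of at least 50% in each baseline drug for six months, "during which no new, long-term antihypertensive medication is introduced and maintained for longer than 14 days". SAP 7.4.2 also states: "The introduction of a new antihypertensive medication with a duration of >14 days will be considered as the end of a benefit duration period".

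The second sensitivity analysis in SAP 7.9 will "treat subjects who begin a new antihypertensive medication following therapeutic dosing that continues for at least 14 days as non-responders".

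Protocol Appendix V lists antihypertensives by class, as examples and expressly not as a complete list. The SAP does not tie that list to the endpoint.

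**The concern.** The endpoint is meant to show a lasting fall in the need for blood-pressure-lowering treatment. If a drug belongs to the antihypertensive set only when its recorded use is hypertension, a drug that lowers blood pressure but is recorded for something else falls outside every rule quoted above.

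Such indications are foreseeable in this disease. The symptom questionnaire in Protocol Appendix IV asks "Have you experienced palpitations" and also covers raised heart rate, tremor and chest pain. Appendix V includes beta-blockers, calcium-channel blockers, diuretics and ACE inhibitors.

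Suppose a baseline alpha-blocker is halved at Month 2, and a beta-blocker is started the same day, recorded for palpitations and continued for nine months. The subject may then be scored a responder although one blood-pressure-lowering drug has partly replaced another. The sensitivity analysis aimed at new drugs might not notice, because it uses the same term. The trial is open-label (Protocol 10.5), so indication is recorded by people who know the treatment and the clinical course.

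**Working it through.** **Tracing the label through the plan**

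1. SAP 7.3.2: a dual-purpose drug used for a non-hypertensive reason leaves the antihypertensive listing. The stated reason for the split is that these drugs measure efficacy.
2. SAP 7.7: daily-dose coding for the analysis datasets starts from the CRF identification. A drug not so identified gets no coded daily dose, unless it is an analgesic for pain.
3. SAP 7.4.1 and 7.4.2: the 50% reduction, the 14-day new-drug rule and the end of benefit refer only to antihypertensive medication.
4. SAP 7.9: the new-drug sensitivity analysis uses the same term. The other one changes only the time window.
5. Protocol 11.4: the stated check is site-monitor review of documentation. No class rule or independent adjudication of indication appears.

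Steps 1 and 2 do not say outright that the endpoint is computed from this filtered set. It is the natural reading, and nothing in the documents contradicts it.

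**The plan's own sample size**

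Inputs from SAP section 6: p0 = 0.10, p1 = 0.25, one-sided alpha 0.025, power 0.90.

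n = [(1.960 × √(0.10 × 0.90) + 1.282 × √(0.25 × 0.75)) / 0.15]² = 58.06. Approximate power at 58 is 0.8998, so the stated 58 reproduces.

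**Success thresholds**

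SAP 7.4.1 uses the Agresti-Coull interval and requires a lower limit above 0.10. With z = 1.96, ñ = n + z² and p̃ = (x + z²/2)/ñ, the lower limit is p̃ − z√(p̃(1 − p̃)/ñ).

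- n = 58: 11 responders give 0.108; 10 give 0.094.
- n = 68: 12 give 0.102; 11 give 0.091.
- n = 75: 13 give 0.103; 12 give 0.092.

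The planned sample is 58 and about 75 are to be enrolled. The 68 is an assumed intermediate size for the Full Analysis Set.

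**How many classifications would matter**

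At the design rate of 25%, the expected count is 14.5 of 58, 17 of 68 or 18.75 of 75. Turning success into failure takes 4 to 5 reclassified responders at 58 (14 − 11 + 1 = 4; 15 − 11 + 1 = 5), 6 at 68 (17 − 12 + 1) and 6 to 7 at 75 (18 − 13 + 1; 19 − 13 + 1). One to three subjects decide the outcome only when the count is already close to the threshold.

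**Illustration on assumed rates**

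Assume a true response rate of 0.10 and that a share q of true non-responders is scored as success through this route. The observed rate is 0.10 + 0.90q. The exact binomial probability of trial success is:

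- n = 58: 2.7% (q = 0), 7.5% (q = 2%), 21.3% (q = 5%), 55.6% (q = 10%).
- n = 75: 3.4%, 10.0%, 28.8%, 68.9% for the same q.

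The documents give no value of q. These figures show sensitivity to the assumption; they do not estimate bias. At a true rate of 0.25 the probability of success is already 89.0% at n = 58 without any misclassification.

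**The case against.** The strongest reply has four parts.

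- SAP 7.3.2 is about listings, and it turns on what a drug was actually used for. The CRF and its completion guidelines are not among the documents, so the antihypertensive flag might follow drug class or a dedicated page. This stands, and it is why the conclusion says may.
- Indication is part of the design. Inclusion criterion 6 requires a stable regimen for tumor-related hypertension, and SAP 7.4.2 describes the outcome as chronic control of hypertension. This also stands: an indication-based primary definition is defensible, and a class-based count answers a somewhat different question.
- There are safeguards. Protocol 11.4 requires evaluation by the investigator and the referring physician, with monitor review. Blood pressure is measured at each change of antihypertensive therapy (11.5.13). All medications are recorded (11.5.3), the non-antihypertensive ones are tabulated by ATC4 and listed, and by-subject figures overlay blood pressure on antihypertensive use. These would make substitution visible to a careful reader, but none re-scores the endpoint.
- Some routes are narrow. Cardiac arrhythmia is an exclusion criterion, and labetalol is barred throughout. Neither prevents another drug being started later for palpitations.

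A reader might also infer that a baseline drug whose recorded indication changes after dosing would look discontinued. No passage describes such changes, so that remains speculation.

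**Conclusion.** The gap holds in conditional form. On the natural reading of SAP 7.3.2, 7.4.1, 7.4.2, 7.7 and 7.9, a new long-term blood-pressure-lowering drug recorded for a non-hypertensive indication may neither end benefit nor enter the new-drug sensitivity analysis. No planned analysis would show how far the result depends on that.

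Three stronger conclusions are tempting but unsupported. The documents do not show that the plan definitely scores such a subject as a responder, because the rule behind the CRF flag is not visible. They do not show that labelling errors run mainly toward success: this route can only add responders, but a drug wrongly flagged as antihypertensive works the other way. And they do not show that the trial's conclusion is at risk, because no frequency is given and the thresholds of 11/58, 12/68 and 13/75 leave a margin of several subjects at the design rate. The matter is decisive only near the threshold. This supports adding a sensitivity analysis and leaving the primary definition unchanged.

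**What to change.** Add to SAP 7.9, before database lock, a third sensitivity analysis of the primary endpoint in the Full Analysis Set:

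- Antihypertensive status is set by drug class, using the WHO-Drug ATC codes already assigned. The code list covers at least the Protocol Appendix V classes and their combinations; Appendix V alone is not enough, because it is not exhaustive. If a substance can carry more than one ATC code, the choice must not depend on indication.
- Any such drug newly started after Therapeutic Dose 1 and taken for more than 14 days ends the benefit period, whatever its recorded indication. The other rules in 7.4.2 stay as they are.
- Each baseline antihypertensive is assessed on its total daily dose across all recorded indications.
- The SAP 7.7 dose coding is extended to these drugs.
- Each subject whose responder status differs from the primary analysis is listed, with the recorded indication.

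The cost is SAP wording, dose coding for additional drugs already in the medication data, one table and one listing. No visit, treatment or data collection changes. The drawback is that drugs genuinely started for a reason other than blood pressure count against the subject. The analysis should therefore be labelled in advance as a conservative bound and read beside the primary result.

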7.3.3. SSKI Administration

In addition to being included in the listing of concomitant medications, administration of potassium iodide (SSKI) administered corresponding with each dose of iobenguane I131 will be presented in a separate listing.

7.4. Efficacy

The primary efficacy endpoint in this study is the proportion of subjects with a reduction (including discontinuation) of all antihypertensive medications by at least 50% for at least six months or two cycles of iobenguane I131.

The Full Analysis Set will be used in the primary analysis and the Per Protocol Set will be used in the secondary analysis of the primary endpoint.

7.4.1. Primary Analysis: Reduction in Use of Antihypertensive Medication

The primary endpoint for this trial is the proportion of study subjects with a reduction (including discontinuation) of all antihypertensive medication by at least 50% for at least six months or two cycles of iobenguane I 131. The 50% reduction is determined separately for each baseline medication, based on the total daily dose of the antihypertensive medication(s) on the day of the first therapeutic dose.

A benefit duration period is measured by maximum duration as follows. The benefit duration period commences when the subject's medication is reduced to a level below 50% of baseline, and continues until the subject's medication rises above 50% of baseline, until the onset of a new antihypertensive medication of >14 days' duration, or to the last subject date as described in section 7.4.2, Primary Endpoint Calculation. A benefit duration period must begin during the 12-Month Efficacy Phase but may end during the Long-term Follow-up Phase. If the subject discontinues participation in the study before the Month 12 efficacy evaluation, the last date for calculation of the duration of benefit is the date of termination in the study.

For purposes of illustration, the following examples are provided (Month refers to the number of 28-day months after the first Therapeutic Dose).

- Example 1: A subject experiences the clinical benefit from the beginning of Month 2 to the beginning of Month 4, and then again from the beginning of Month 5 to the beginning of Month 12. Since the maximum duration of the benefit was 7 months, the subject is considered a success on the primary endpoint.
- Example 2: A subject experiences the clinical benefit from the beginning of Month 2 to the beginning of Month 4, and then again from the beginning of Month 6 to the beginning of

Month 11. Even though the subject experienced the clinical benefit for a total of 7 months, the maximum duration of the benefit was only 5 months, so the subject is considered a failure on the primary endpoint.

- Example 3: A subject experiences the benefit from the beginning of Month 2 to the beginning of Month 9. At Month 10, the subject receives another anticancer treatment and is discontinued from the study. Since the maximum duration of the benefit was 7 months, prior to discontinuation, the subject is considered a success on the primary endpoint.

For the primary analysis of the primary endpoint, a point estimate (with a 95% confidence interval, calculated using the Agresti-Coull method) for the proportion of subjects in the Full Analysis Set with a reduction (including discontinuation) of all antihypertensive medications by at least 50% for at least six months or two cycles will be calculated. This single-arm trial will be considered a success if the lower bound of this two-sided 95% confidence interval exceeds 0.10 (10%).

A listing of response to treatment (yes/no) with supporting information (antihypertensive medications with their dates of use, doses and relative change from baseline) will be presented.

Use of antihypertensive medication over time will be presented graphically by subject. These figures will include the mean systolic and diastolic blood pressure measurements from healthcare providers (either at site visits or at the subject's home) for each visit window. This information will also be presented in a data listing.

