13.3.2 Efficacy Analysis

13.3.2.1 Primary Analysis: Reduction in use of antihypertensive medication

The primary endpoint in this study is the proportion of subjects, after a Therapeutic Dose of Ultratrace iobenguane I 131, with a reduction (including discontinuation) of all antihypertensive medication by at least 50% for at least six months or two cycles. The duration of benefit is measured by maximum duration as follows. A benefit duration period commences when the subject's medication is reduced to a level at or below 50% of baseline, and continues until the subject's medication rises above 50% of baseline. For purposes of illustration, the following examples are provided (Month refers to the number of months after the first Therapeutic Dose).

- Example 1: A patient experiences the clinical benefit from the beginning of Month 2 to the beginning of Month 4, and then again from the beginning of Month 5 to the beginning of Month 12. Since the maximum duration of the benefit was 7 months, the subject is considered a success on the primary endpoint.
- Example 2: A patient experiences the clinical benefit from the beginning of Month 2 to the beginning of Month 4, and then again from the beginning of Month 6 to the beginning of Month 11. The patient begins another anticancer treatment at Month 15 and is discontinued. Even though the patient experienced the clinical benefit for a total of 7 months, the maximum duration of the benefit was only 5 months, so the subject is considered a failure on the primary endpoint.
- Example 3: A patient experiences the benefit from the beginning of Month 2 to the beginning of Month 9. At Month 10, the patient receives another anticancer treatment and is discontinued from the study. Since the maximum duration of the benefit was 7 months, prior to discontinuation, the patient is considered a success on the primary endpoint.

For the primary analysis of the primary endpoint, a point estimate (with a 95% confidence interval, using the normal approximation with a continuity correction) for the proportion of subjects experiencing a reduction (including discontinuation) of all antihypertensive medication

by at least 50% for at least six months or two cycles will be calculated. This single-arm trial will be considered a success if the lower bound of the two-sided 95% confidence interval exceeds 0.10 (10%). The Full Analysis Set will be used for the primary analysis, but this same analysis will be repeated for the Per Protocol Set.

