- b. the date of the subject's last applicable recorded study-related disposition date. If the subject has discontinued the study prior to the end of the 12-Month Efficacy Phase due to any of the following reasons:
- Withdrew consent
 - Was lost to follow-up
 - Death
 - Withdrew due to progressive disease
 - Received other anticancer therapy
 - Experienced an adverse event resulting in study discontinuation

The last participation date is the corresponding disposition date within the 12-Month Efficacy Phase (i.e., date that the subject withdrew consent, was lost to follow-up, died, withdrew due to disease progression, received other anticancer therapy, or experienced an adverse event resulting in study discontinuation).

If the subject has completed the 12-Month Efficacy Phase but continues to meet the criteria of having a $\geq 50\%$ reduction of all antihypertensive medications, the last applicable disposition date would be the long-term follow-up completion/discontinuation date.

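### The SAP gives conflicting rules on whether a dose rise of 14 days or less in an existing antihypertensive ends a primary-endpoint benefit period

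*SAP*

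**What the plan says.** **Stop rule for a dose rise in an existing drug**

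- SAP 7.4.1: the period runs until the subject's "medication rises above 50% of baseline", with no minimum length. The same sentence has a more-than-14-days condition, but it attaches only to a new drug. Protocol 13.3.2.1 also stops benefit at any rise above 50%.
- SAP 7.4.2, criterion 3: each baseline drug must be reduced by at least half for six consecutive months. The only 14-day exception is for new drugs.
- SAP 7.4.2, end date (a): a dose change that breaks the 50% level ends the period only if it is one "that is greater than 14 days in duration and continues without a reduction to the" required level.
- SAP 7.4.2, Consideration 2: a rise of 14 days or less does not disqualify, but this covers only rises over the full baseline dose.

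**Start rule.** SAP 7.4.1 starts benefit when "medication is reduced to a level below 50% of baseline". The protocol has "medication is reduced to a level at or below 50% of baseline". Consideration 5 of SAP 7.4.2 has "reduced to a level of 50% or below the baseline dose for at least six consecutive months in duration". The opening sentence of 7.4.1 and criterion 3 also count exactly 50%.

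**Precedence.** SAP 7.4.1 points to 7.4.2 only for the last subject date. The change log in SAP 9 calls 7.4.2 the endpoint calculation but does not say that it overrides 7.4.1.

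**Length and success.** Six months means 168 days (SAP 7.4.2). The trial succeeds if the Agresti-Coull two-sided 95% lower bound in the Full Analysis Set exceeds 0.10 (SAP 7.4.1).

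**The concern.** Responder status is the whole primary endpoint of an open-label, single-arm trial, so one medication record should give one answer. A programmer working from 7.4.1 or criterion 3 would cut the benefit period at a ten-day rise. One working from end date (a) would count straight through it. The choice would then be made in programming rather than in the plan, and the planned sensitivity analyses would not show its effect.

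**Working it through.** **1. The plan's own figures.** With p0 = 0.10, p1 = 0.25, one-sided alpha 0.025 and power 0.90 (SAP 6):

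n = [1.960·√(0.10·0.90) + 1.2816·√(0.25·0.75)]² / 0.15² = (0.5880 + 0.5549)² / 0.0225 = 58.06.

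This reproduces 58, and it does not depend on the wording at issue.

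The SAP 7.4.1 examples, in 28-day months:
- Example 1 counts 7 × 28 = 196 days and does not bridge a 28-day gap.
- Example 2 counts 5 × 28 = 140 days and does not bridge a 56-day gap. Bridged, it would be 9 × 28 = 252 days. The SAP says "the maximum duration of the benefit was only 5 months, so the subject is considered a failure on the primary endpoint".

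Both gaps exceed 14 days, so the examples do not settle the short-rise case. They also do not name the cause of the gap.

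**2. One record under each rule (illustrative).** One drug is at 25% of baseline from Day 60, at full dose on Days 215–224, and at 25% again until benefit is lost or follow-up ends at Day 365. The rise returns to the baseline dose but does not exceed it, so Consideration 2 does not apply.

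| Rule | Periods | Result (168 needed) |
|---|---|---|
| SAP 7.4.1, Protocol 13.3.2.1, criterion 3 | 215 − 60 = 155; 365 − 225 = 140 | Failure |
| SAP 7.4.2 end date (a) | 365 − 60 = 305 | Responder |

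**3. When the rules differ.** Let s be the start of reduction, r the start of the rise, d its length (14 days or less) and e the end. The results differ if e − s ≥ 168 while r − s < 168 and e − r − d < 168. The span e − s therefore runs from 168 to at most 167 + 14 + 167 = 348 days. In the example (s = 60, d = 10, e = 365), r must be below 228 and above 187. That is Days 188–227, a 40-day window.

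**4. Limit from long-term follow-up.** The SAP says "A benefit duration period must begin during the 12-Month Efficacy Phase but may end during the Long-term Follow-up Phase". For a subject who completes 12 months still reduced, "the last applicable disposition date would be the long-term follow-up completion/discontinuation date". If the reduction in the example lasted to Day 225 + 168 = 393, the second part alone would qualify and both rules would give a responder.

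**5. SAP 7.9 does not show the difference.** Its first analysis requires the six months to be completed within the 12-month efficacy period. Under end date (a) the example reaches 168 days on Day 60 + 168 = 228, so it stays a responder. The second analysis concerns new drugs, and the example has none.

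**6. Trial-level threshold.** The Agresti-Coull lower bound is p̃ − 1.96·√[p̃(1 − p̃)/ñ], with ñ = n + 3.84 and p̃ = (x + 1.92)/ñ. At n = 58, ñ = 61.84:
- x = 10: p̃ = 0.1928, lower bound 0.0944 (not a success).
- x = 11: p̃ = 0.2089, lower bound 0.1076 (success).

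Protocol 13.2 places the 58 in the Per Protocol Set and expects about 75 enrolled, so the Full Analysis Set may be larger. The minimum is 11 for n = 55–62, 12 for n = 63–69 and 13 for n = 70–77.

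**7. Start wording.** A dose held at exactly 50% of baseline for 201 days gives 0 benefit days under the literal 7.4.1 start rule. It gives 201 days under 7.4.2 and the protocol.

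**The case against.** The best defence is that SAP 7.4.2 plainly governs. It is the calculation section, it fixes the 168-day count, and it gives dated start and end rules. Its rationale, chronic control rather than transient catecholamine release, favours tolerating short rises. Protocol 13.5 lets the final SAP change the protocol analysis, so differing from the protocol is not in itself an error. Doses and dates are listed by subject, so an affected record would be visible.

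Most of this is fair, but it does not remove the conflict. A reader might infer that 7.4.2 is uniformly lenient and 7.4.1 strict, so that naming 7.4.2 as governing would be enough. The text does not support that, because criterion 3 of 7.4.2 read literally sides with 7.4.1. The conflict therefore also lies inside 7.4.2, and the 305-day result rests on end date (a) alone. Listings make a record visible but do not say how to classify it.

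A reader might also infer that end date (a) lets a long rise that is later reversed be bridged. Consideration 5 largely answers this. After a rise of more than 14 days over the baseline dose, it sets the start of response at the date the last drug is back at half or less, so the clock restarts. Examples 1 and 2 point the same way. What remains is a minor clarification for long rises that stay at or below the baseline dose.

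**Conclusion.** The point holds for dose rises of 14 days or less in an existing drug. SAP 7.4.1, criterion 3 and the protocol end the period or require it to be unbroken. End date (a) does not, and nothing ranks the rules. This should be fixed before analysis.

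The size is bounded. A single short rise changes a subject's status only when the reduced span is 168 to 348 days and neither part reaches 168. It changes the trial result only if the responder count sits at the threshold, 11 at n = 58. The example record is constructed, and the documents give no frequency for such records. They therefore do not support an inference that many subjects would be reclassified or that the trial result is unreliable.

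A reader might also take the start wording in 7.4.1 as a deliberate tightening. It stands alone against the endpoint definition in the same section, 7.4.2 and the protocol, so it is a drafting slip. It still needs correcting, because halving a dose lands exactly on the boundary. The new-drug stop rule is the same in both SAP sections and is not in question.

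**What to change.** 1. In SAP 7.4.1, replace the start wording with the protocol's, "medication is reduced to a level at or below 50% of baseline".
2. State one identical stop rule for dose rises of existing drugs in SAP 7.4.1, criterion 3 of 7.4.2 and end date (a) of 7.4.2. Saying only that 7.4.2 governs is not enough, because criterion 3 and end date (a) would still disagree.
3. When rewording end date (a), make clear that a rise of more than 14 days that is later reversed ends the period and restarts the clock, consistent with Consideration 5 and Examples 1 and 2.
4. Add to SAP 7.9 one sensitivity analysis using the protocol's stop rule, under which any rise above 50% of baseline ends benefit.

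The cost is a few wording changes and one extra table. No new data are needed, because SAP 7.4.1 already lists antihypertensive doses and dates by subject.
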